7.4.3 Response to Hypoglycemia

- Patients are encouraged to check their BG for any symptoms of hypoglycemia.
- Patients will be permitted to take 15 grams of carbohydrates for any BG value <60 mg/dL. Trial staff will ensure proper functioning of the BP, infusion set, and insulin pump, and will encourage the patient to wait for the BP to treat the low blood sugar for as long as they feel comfortable.
- Patients will be required to take 15 grams of carbohydrates for any BG value <50 mg/dL. After treatment of hypoglycemia, a follow-up measurement will be taken 15 minutes later. Repeated measurements will be taken every 15 minutes until the BG is >60 mg/dL. Treatment will be repeated if subsequent BG values are still <50 mg/dL. All carbohydrate treatments for hypoglycemia will be documented by trial staff (amount and time).
- Trial staff will check the infusion site, BP, and insulin pump for normal operation any time hypoglycemia occurs. If there is any suspicion of infusion set malfunction, the site should be replaced. Trial staff will check the BP for any malfunction and correct any problems that are found.
- If no correctable fault is found, but there is doubt regarding the correct function of the BP system, an entirely new backup BP system may be started.
- If a patient experiences a seizure or unconsciousness associated with hypoglycemia, his or her participation in the trial will be discontinued.

7.4.4 Response to Hyperglycemia

- Trial staff will check the infusion site, BP, and insulin pump for normal operation any time BG is >300 mg/dL. If there is any suspicion of infusion set malfunction, the site should be replaced. Trial staff will check the BP for any malfunction and correct any problems that are found. If the BG remains >300 mg/dL for 2 hours despite troubleshooting, blood ketones will be measured. If the blood ketone result is >1.5 mmol/L, the visit will be stopped and rescheduled. The patient will be provided with insulin and a syringe to give an injection based on their correction factor.
- If a patient experiences diabetic ketoacidosis, his or her participation in the trial will be discontinued.
- If no correctable fault is found, but there is doubt regarding the correct function of the BP system, the treatment visit may be stopped and the visit rescheduled.

7.4.5 Response to Nausea/Vomiting

If significant nausea (e.g., that prevents the patient from eating normally) or any vomiting occurs, trial staff will notify the Investigator. Trial staff will assist the patient in troubleshooting, such as checking BG and the calibration of the CGM (excessive glucagon dosing may occur if the CGM is reading lower than the true BG). If a patient experiences persistent nausea and vomiting thought to be related to glucagon dosing, his or her participation in the trial will be discontinued.

Clinical Trial Protocol
ZP4207-16051

Version number: 6.0
Amendment 5.0
Date: 09 September 2016

7.4.6 Response to Other Medical Needs

If patients experience urgent or emergent medical concerns outside the scope of diabetes care and their primary care physicians, they will be taken to the MGH walk-in clinic or emergency room, or if necessary call 911.

7.4.7 Monitoring of Bionic Pancreas Performance

Bionic pancreas inventors and developers [REDACTED], [REDACTED], and/or an engineer trained by them will be readily available by phone for consultation for the trial staff at all times during the course of the trial.

7.4.8 Supervision by Trial Staff

A trial MD will be on call at all times during the course of the trial. An RN or MD will be with the trial patients in the Diabetes Research Center at all times.

7.5 Anti-drug Antibodies Assessment Visit (Visit 5)

Patients will return for an ADA Assessment Visit 10 days \pm 3 days following the last day of dosing (Visit 4) for ADA sampling and a review of AEs and concomitant medications.

7.6 Follow-up Visit (Visit 6)

Patients will return for a Follow-up Visit 25 days \pm 4 days following the last day of dosing (Visit 4), for chemistry, hematology, and ADA sampling, and a review of AEs and concomitant medications.

8 ENDPOINTS

8.1 Primary Endpoint

The primary endpoint is the safety and tolerability of ZP4207 in the BP using either the iLet or the iPhone platform as assessed by:

- Number and type of AEs
- Clinical laboratory measurements
- Vital signs
- 12-lead ECG
- Local tolerability and infusion site reactions as measured with the Draize scale
- Immunogenicity as measured by ADA
- Pain as measured on a 10 cm VAS
- Nausea as measured on a 10 cm VAS

8.2 Secondary Endpoints

The secondary endpoints include measurements of BP function as well as glycemic and non-glycemic measurements.

Clinical Trial Protocol
ZP4207-16051

Version number: 6.0
Amendment 5.0
Date: 09 September 2016

8.2.1 **Bionic Pancreas Function**

This endpoint data will be generated from the BP data during each treatment visit:

- Average percent insulin dose amounts calculated by the BP control algorithm that are successfully delivered by the pump
- Average percent glucagon/ZP4207 dose amounts calculated by the BP control algorithm that are successfully delivered by the pump
- Average percent dose amounts successfully issued to the pump by the BP control algorithm that are successfully delivered by the pump (calculated doses are not issued unless the pump is accessible and its delivery channel is available)
 - Average percent insulin dose amounts successfully issued to the pump by the BP control algorithm that are successfully delivered by the pump
 - Average percent glucagon/ZP4207 dose amounts successfully issued to the pump by the BP control algorithm that are successfully delivered by the pump
- Average percent dose amounts calculated by the BP algorithm that are successfully issued to the pump by the BP (calculated doses are not issued unless the pump is accessible and its delivery channel is available)
 - Average percent insulin dose amounts calculated by the BP control algorithm that are successfully issued by the BP
 - Average percent glucagon/ZP4207 dose amounts calculated by the BP control algorithm that are successfully issued by the BP
- Average percent of 5-minute steps during which the BP is functioning nominally in all respects based on real-time CGM data (new CGM glucose reading captured, dose calculated, and dose issued to pumps)
- Average percent of 5-minute steps during which the BP is functioning nominally with or without a new CGM glucose reading captured (dose calculated and dose issued to pumps). If a CGM signal is not available, the dose calculated may be based on weight or historical basal rates.
- CGM reliability index, calculated as percent of possible values actually recorded by CGM
- CGM Mean Absolute Relative Difference versus time-stamped BG values from meter download
- List of technical faults associated with the BP including cause and resolution

8.2.2 **Glycemic**

All of following metrics will be generated from the Dexcom G4 Platinum CGM data during each treatment visit:

- Fraction of time spent within each of the following glucose ranges:
 - <50 mg/dL
 - <60 mg/dL
 - <70 mg/dL
 - 70-120 mg/dL
 - 70-140 mg/dL
 - 70-180 mg/dL
 - >180 mg/dL
 - >250 mg/dL
 - >300 mg/dL
- Number of severe hypoglycemic events (patients unable to self-treat, requiring the assistance of another person)

Clinical Trial Protocol
ZP4207-16051

Version number: 6.0
Amendment 5.0
Date: 09 September 2016

- Number of episodes of symptomatic hypoglycemia
- Number of carbohydrate interventions for hypoglycemia
- Total grams of carbohydrates taken for hypoglycemia
- Mean CGM glucose

8.2.3 **Non-glycemic**

- Glucagon/ZP4207 total delivery per kg of body mass
- Insulin total delivery per kg of body mass
- Number of unscheduled infusion set replacements
- Number of unscheduled CGM sensor changes

9 **LABORATORY ASSESSMENTS**

Descriptions of sample handling and sample processing, storage, and shipment at the site will be included in the laboratory manual.

The responsible laboratories are listed in the [address list](#).

9.1 **Safety Laboratory Assessments**

Chemistry and hematology samples will be collected at specified time points. See [Appendix A](#) for the schedule of procedures and [Appendix B](#) for a list of clinical laboratory analytes.

9.2 **Pharmacodynamic Assessments (Plasma Glucose)**

At Visit 3 and Visit 4, plasma glucose samples will be taken from the IV at least hourly in parallel with ZP4207/glucagon exposure sampling and measured using the YSI 2300 STAT Plus. If the YSI 2300 STAT Plus and/or IV fails, the Nova StatStrip Xpress will be used for glucose measurements. If BG is <150 mg/dL, then sampling will be every 30 minutes. If BG is <100 mg/dL, then sampling will be every 20 minutes. If BG is <80 mg/dL, then sampling will be every 10 minutes. The actual time of sampling will be recorded in the eCRF.

9.3 **Exposure Assessments (ZP4207 and Glucagon)**

At Visit 3 and Visit 4, ZP4207/glucagon exposure sampling will be collected at least hourly. If BG is <150 mg/dL, more frequent samples for plasma ZP4207/glucagon may be drawn at the discretion of the Investigator. The actual time of sampling will be recorded in the eCRF.

Bioanalytical Reports will be prepared.

9.4 **Anti-drug Antibodies Assessments**

Blood samples (including back-up samples) for serum anti-ZP4207 and anti-glucagon antibodies will be taken at Visit 3, the ADA Assessment Visit (Visit 5), and the Follow-up Visit (Visit 6). Any patient that tests positive for ADA will be monitored until the ADA levels return to baseline.

Bioanalytical Reports will be prepared.

Clinical Trial Protocol
ZP4207-16051

Version number: 6.0
Amendment 5.0
Date: 09 September 2016

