6.7 Other Trial Devices

YSI 2300 STAT Plus™ (Yellow Springs Instruments): The YSI 2300 STAT Plus is an FDA-approved glucose analyzer. Blood glucose measurements using the YSI 2300 STAT Plus will be obtained off of the intravenous (IV) line during both treatment visits.

Nova Biomedical StatStrip Xpress Glucose Meter: The Nova StatStrip Xpress glucose meter is an FDA-approved glucose meter that is commercially available. Blood glucose measurements for CGM calibration will be obtained with the Nova StatStrip Xpress during both treatment visits if the YSI 2300 STAT Plus fails and via fingerstick with the Nova StatStrip Xpress during any periods when IV blood samples are not available for any reason or the IV fails.

Exercise Bike: The trial will utilize a stationary exercise bike (ergometer) for the in-clinic exercise at the treatment visits. This bike will be stored at the Diabetes Research Center when not in use.

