- Patients will exercise on a stationary bike with a heart rate from 120-140 beats per minute for a total of 4,000 heart beats (approximately 30 minutes). Patients will rate their exercise intensity using the Borg scale every 5 minutes, with the target intensity level between 12 and 14. Heart rate will be measured every 5 minutes.
- BG measurements will be obtained off of the IV line every 10 minutes. If BG is <80 mg/dL, BG measurements will be obtained off of the IV line every 5 minutes.
 - Carbohydrates will be given for any BG <50 mg/dL according to the following protocol: Dextrose (g) = BSA (m²)/[1.7 m² (women) or 1.9 m² (men)] *15 g.
 - Repeat treatments will be given at 15-minute intervals as long as BG remains <50 mg/dL.
- If there is an interruption in the Dexcom CGM output, trial staff will assist the patient in recovering CGM data streaming. If this requires replacement of the CGM sensor, BGs will be checked every 10 minutes (every 5 minutes if BG is <80 mg/dL) using blood from the IV until the CGM is able to be calibrated again. These BGs will be entered into the BP, which will treat them as CGM values and dose insulin and/or glucagon appropriately.
- If there is a complete failure of the BP operation, patients will take over their own BG control using their personal insulin pump until the BP can be brought back online. If BP control cannot be promptly resumed (e.g., within 30 minutes), the patient may be asked to repeat that trial day once.
- Patients may choose to withdraw from the trial at any time. If they withdraw from the trial, they should alert a provider immediately.
- Just prior to the end of the study visit, vital signs including body temperature and blood pressure will be obtained and a 12-lead ECG will be performed.
- After approximately Hour 8, but not earlier than at least 60 minutes after end of exercise, the BP will be stopped and the patient will continue with their personal insulin pump.

Clinical Trial Protocol
ZP4207-16051

Version number: 5.0
Amendment 4.0
Date: 02 September 2016

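### CGM accuracy (MARD) is referenced to meter readings, although the meter is only the fallback glucose method at the treatment visits

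*Protocol*

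**What the plan says.** Section 8.2.1 (version 6.0) introduces the device-function endpoints with "This endpoint data will be generated from the BP data during each treatment visit" and lists among them "CGM Mean Absolute Relative Difference versus time-stamped BG values from meter download".

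Section 9.2 (version 6.0) sets the glucose method for Visits 3 and 4: "samples will be taken from the IV at least hourly in parallel with ZP4207/glucagon exposure sampling and measured using the YSI 2300 STAT Plus". Sampling becomes more frequent as glucose falls. The meter's role comes next: "If the YSI 2300 STAT Plus and/or IV fails, the Nova StatStrip Xpress will be used for glucose measurements".

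The device and visit-procedure sections are available only in version 5.0 text, and they agree. Section 6.7 says of the meter: "Blood glucose measurements for CGM calibration will be obtained with the Nova StatStrip Xpress during both treatment visits if the YSI 2300 STAT Plus fails". It adds meter fingersticks for times when blood cannot be drawn from the line. In the exercise part of Section 7.4.1, "BG measurements will be obtained off of the IV line every 10 minutes". Section 6.7 describes the YSI as an analyzer and the Nova as a meter, and Section 7.4.1 has the BP and glucose meters downloaded after the visit.

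**The concern.** The endpoint names the backup device as its reference. If the YSI and the IV line work, the schedule plans no meter reading after the BP starts. The meter readings that do arise would come mainly from times when something had gone wrong, so they would not represent sensor accuracy over the visit. The regular laboratory-type series collected at the same visits would play no part in this endpoint.

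Sensor accuracy matters here because the CGM drives dosing and supplies every time-in-range metric in Section 8.2.2. MARD is the listed endpoint that measures it. This is not detail left to the SAP. The protocol fixes the reference, so an SAP that follows it inherits the problem, and one that uses YSI values departs from the protocol's definition.

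**Working it through.** The protocol states no figure for this endpoint (no sample size, power or expected number of pairs), so there is none to reproduce. The check compares the sections and counts planned reference values.

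**Inputs**
- Endpoint window: each treatment visit (Section 8.2.1, version 6.0).
- Routine method: YSI at least hourly, and every 30 minutes when BG is below 150 mg/dL (Section 9.2, version 6.0).
- Visit length: about 8 hours of BP operation (Section 7.4.1, version 5.0).
- Patients: 20 to 24 randomized (Section 11.2.4, version 6.0), two treatment visits each, so 40 to 48 visits. Up to 10 are expected to complete each part (Section 3.3, version 5.0).
- Share of samples falling back to the meter: not given. Values of 2%, 5% and 10% are assumed.

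**Planned YSI values**
- Hourly, Hours 0 to 8: 8 + 1 = 9 per visit.
- Per arm per part with 10 completers: 9 × 10 = 90.
- Whole trial: 9 × 40 = 360 to 9 × 48 = 432.
- If BG stayed below 150 mg/dL, the 30-minute schedule gives 8 × 2 + 1 = 17 per visit, or 680 to 816 in total.
- Each value forms a pair only if a CGM reading exists at that time, so these are planned counts, not guaranteed pairs.

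**Meter values from fallback on the hourly schedule** (share × 9 × visits)

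| Assumed share | Per visit | 40 visits | 48 visits |
|---|---|---|---|
| 0% | 0 | 0 | 0 |
| 2% | 0.18 | 7.2 | 8.6 |
| 5% | 0.45 | 18 | 21.6 |
| 10% | 0.9 | 36 | 43.2 |

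**Pairing.** Section 11.2.2 compares arms within patient. Suppose a proportion p of visits contains a failure, independently between visits. The expected number of patients with fallback meter values at both visits is n × p². At p = 10% this is 20 × 0.01 = 0.2 to 24 × 0.01 = 0.24 patients. At p = 20% it is 0.8 to 0.96. These totals cover both parts, which are analysed separately.

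**Calibration values.** Section 6.7 (version 5.0) makes the meter the calibration source only if the YSI fails or IV blood is unavailable, so some YSI values will also be calibration inputs. Section 7.4.1 (version 5.0) adds a calibration during the visit when the CGM is off by 15 mg/dL or more at BG below 75 mg/dL, or by 20% or more above 75 mg/dL, provided the moment is suitable. Since 15/75 = 20%, both limits imply an absolute relative difference of at least 20%. Deleting such a pair lowers MARD whenever the mean of the remaining pairs is below 20%. The CGM reading taken just before the calibration has not yet been adjusted to that value, so it remains a valid comparison.

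**The case against.** The strongest reply is that meter use during a visit is not confined to equipment failure. Section 7.4.3 (version 6.0) encourages BG checks for symptoms without naming a device. Section 7.4.1 (version 5.0) leaves the device for the arrival BG and visit-start calibration unnamed. Section 6.7 (version 5.0) allows fingersticks whenever IV blood is unavailable for any reason. Section 6.6 (version 5.0) says the iLet communicates automatically with the Nova meter. This stands: the number of meter values is unknown, and no failure rate is given. A reader might infer that there would be no meter values, or almost none, but the documents do not support a count. They do support saying that such values would be unscheduled and selected.

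A reader might also infer that the endpoint is circular because the meter holds the patient's calibration readings from the night before. Those fall outside the endpoint's window, so the definition already excludes them.

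It is fair, too, that MARD is one of many secondary device measures, that no sample size depends on it, and that the YSI series is used elsewhere, as the pharmacodynamic measure in Section 9.2. These points limit the importance of the mismatch. Nothing in the text available for review reconciles Sections 8.2.1 and 9.2.

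**Conclusion.** The mismatch holds within version 6.0 itself: Section 8.2.1 takes its reference from a device that Section 9.2 uses only as a fallback. As written, MARD would rest on few, selected values, with little or no scope for a paired comparison between arms. The alternative is about 9 or more YSI values per visit, up to about 90 per arm per part on the hourly schedule.

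The figure of 90 assumes 10 completers, an 8-hour visit and a concurrent CGM reading each time. The meter figures assume a fallback share of 0% to 10% and exclude any symptom-prompted or arrival checks made on the meter. The supporting text from Sections 3.3, 6.6, 6.7 and 7.4.1 is from version 5.0, because those sections of version 6.0 were not available for review. The effect is confined to a secondary device-function endpoint. The correction should be made, but the primary safety endpoint does not depend on it.

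**What to change.** In Section 8.2.1, redefine the endpoint as CGM MARD versus time-matched YSI plasma glucose during each treatment visit. Use Nova values only where YSI or IV values are unavailable, and flag them so that results with and without them can be shown.

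Where a reference value was also used to calibrate the CGM, keep it and pair it with the CGM reading immediately before that calibration. Do not exclude it: calibrations added during the visit are triggered by large CGM error, so exclusion would bias MARD downward.

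The cost is one line in the protocol, matched in the SAP. No new sample or procedure is needed. Section 7.4.2 already collects every BG measurement, and Section 9.2 records actual sampling times in the eCRF. The protocol does not say where the YSI results themselves are stored, so data management should confirm that they can be merged with the CGM record by time.

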10 SAFETY REPORTING

10.1 Adverse Events

An AE is any untoward medical occurrence in a trial patient administered an IMP and which does not necessarily have a causal relationship with the treatment. An AE can therefore be any unfavorable and unintended sign (e.g., an abnormal laboratory finding), symptom, or disease temporally associated with the use of an IMP, whether or not considered related to the IMP. Patients should be instructed to report any AE they experience to the Investigator. Note: This includes events from the first trial-related activity from Visit 3.

AEs for ZP4207 include:

- A clinically significant worsening of a concomitant illness
- A clinical laboratory abnormality which is clinically significant, i.e., any abnormality that suggests a disease and/or organ toxicity and is of a severity that requires active management. Active management includes active treatment or further investigations, for example, change of medicine dose or more frequent follow-up due to the abnormality.
- Hypoglycemic episodes
- Injection site reactions

The following should **not** be recorded as AEs, if recorded prior to randomization (on the Screening Form or the eCRF):

- Pre-planned procedure, unless the condition for which the procedure was planned has worsened from the first trial-related activity from Visit 3.
- Pre-existing conditions found as a result of screening procedures (pre-existing conditions should be reported as medical history or concomitant illness).

For known (listed) AEs for Glucagon and Humalog, please refer to SPC for [Glucagon](#) and [Humalog](#).

10.1.1 Follow-up of Adverse Events

All AEs that are ongoing at the end of the patient's participation in the trial will be followed-up until the event is resolved or reaches a satisfactory outcome as deemed by the Investigator. Follow-up actions for all serious adverse events (SAEs) will be performed according to appropriate clinical care practices and may depend on the nature of the event. These will be determined after internal review and/or Sponsor review. The follow-up information should only include new (updated and/or additional) information that reflects the situation at the time of the Investigator's signature.

Follow-up information on (S)AEs will be updated using the (S)AE Form. If a non-serious event becomes serious during the follow-up, the AE Form and SAE Form must be used and reporting timelines follow those of an SAE.

The Investigator must forward follow-up information on SAEs, and if previously non-serious AEs become SAEs, to the Sponsor.

Clinical Trial Protocol
ZP4207-16051

Version number: 6.0
Amendment 5.0
Date: 09 September 2016

10.1.2 **Precautions**

Normal precautions taken for a human trial will be taken during this trial. Qualified and well-trained physicians and medical staff will instruct the patients. During a patient's participation in the trial, the Investigator should ensure that adequate medical care is provided to the patient for any AEs, including clinically significant laboratory values related to the trial. The Investigator should inform the patient when medical care is needed for intercurrent illnesses of which the Investigator becomes aware.

For further information on safety precautions for ZP4207, Lilly glucagon, and Lilly Humalog, please refer to the current version of the Investigator's Brochure (IB) for ZP4207 ([Zealand Pharma A/S, 2015](#), or any updates hereof), and the SPC for Glucagon ([Eli Lilly, 2012](#)) and Humalog ([Eli Lilly, 2015](#)), respectively.

10.1.3 **Assessment of Adverse Events by the Investigator**

Intensity of an Adverse Event

The maximum intensity (severity) of all AEs must be assessed by the Investigator and documented. Severity should be graded when the AE outcome is known:

- **Mild:** A type of AE that is usually transient and may require only minimal treatment or therapeutic intervention. The event does not generally interfere with usual activities of daily living.
- **Moderate:** A type of AE that is usually alleviated with additional specific therapeutic intervention. The event interferes with usual activities of daily living, causing discomfort but poses no significant or permanent risk of harm to the patient.
- **Severe:** A type of AE that interrupts usual activities of daily living, or significantly affects clinical status, or may require intensive therapeutic intervention.

A "severe" reaction does not necessarily deem the AE as "serious," and an SAE may not be "severe" in nature.

Causality Relationship to IMP

Insulin (insulin lispro, Lilly Humalog), glucagon (glucagon for injection, Eli Lilly), and ZP4207 are all regarded as IMP.

The causality of each AE should be assessed by the Investigator according to the following classification:

- **Related:** Good reason and sufficient documentation to assume a causal relationship.
- **Not related:** No relationship to trial product can be established.

Outcome of an Adverse Event

The outcome of all AEs must be assessed by the Investigator and documented by his/her staff. The following definitions should be used:

- **Recovered/resolved:** The patient has fully recovered, or by medical or surgical treatment the condition has returned to the level observed at the first trial-related activity from Visit 3.
- **Recovering/resolving:** The condition is improving and the patient is expected to recover from the event. This term is only applicable if the patient has completed the trial.

Clinical Trial Protocol
ZP4207-16051

Version number: 6.0
Amendment 5.0
Date: 09 September 2016

- **Recovered/resolved with sequelae:** The patient has recovered from the condition, but with lasting effect due to a disease, injury, treatment, or procedure. If a sequela meets an SAE criterion, the AE must be reported as an SAE.
- **Not recovered/not resolved:** The condition of the patient has not improved and the symptoms are unchanged, or the outcome is not known.
- **Fatal:** This term is only applicable if the patient died from a condition related to the reported AE. Outcomes of other reported AEs in a patient before he/she died should be assessed as “recovered/resolved,” “recovering/resolving,” “recovered/resolved with sequelae,” or “not recovered/not resolved.” An AE with a fatal outcome must be reported as an SAE.
- **Unknown:** This term is only applicable if the patient is lost to follow-up.

